approx. = approximately EC = endometrial carcinoma; HNSCC = squamous cell carcinoma of head and neck; Mel = melanoma (excluding uveal); MTD = maximum tolerated dose; NSCLC = non-small cell lung cancer; ORR = objective response rate; RCC = renal cell carcinoma (predominantly clear cell), UC = urothelial carcinoma;

- a: Based on the efficacy and safety results from the first 10 subjects in each cohort, an additional 10 subjects may be enrolled for a total of 20 subjects in each cohort.
- b: The endometrial and renal cell carcinoma cohorts may be expanded to approximately 120 and 145 evaluable subjects, respectively.
- c: This RCC subset includes previously treated subjects who have received 1 or 2 prior therapies and have progressed on treatment with an anti-programmed cell death protein 1 (PD)-1/ PD-1 ligand 1 (PD-L1) mAb.

Once they complete the Treatment Phase, each subject still receiving study treatment will transition into the Extension Phase. Tumor assessments will continue during the Treatment Period of the Extension Phase. As of Amendment 09, subjects in the treatment period of the extension phase who discontinue pembrolizumab for any reason and remain on lenvatinib study treatment will transition to lenvatinib commercial supply if local country regulations permit. As of Amendment 09, tumor assessments will continue during the Extension Phase as per the local standard of care but not less frequent than every 6 months. Tumor assessments will not be performed or collected during the Follow-Up period of the Extension Phase. Subjects who undergo the Off-Tx visit will undergo safety follow-up for AEs for 30 days from the last dose of study treatment. Serious adverse event (SAEs) will be collected for 90 days after the last dose or 30 days following the last dose if the subject initiates new anticancer therapy, whichever is earlier. Transition to commercial lenvatinib will be considered new anticancer therapy. After the end of the safety follow-up period, no data will be collected subsequently. The data cutoff for each Phase 2 cohort will occur when the evaluable subjects in that cohort complete 8 cycles of treatment or discontinue early.

The study will be conducted in 3 phases: a Pretreatment Phase, a Treatment Phase, and an Extension Phase.

The definition of the end of the study for each cohort is the time of data cutoff for the final analysis or the time of last subject/last treatment, whichever occurs later.

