9.1.3.2 Follow-Up Period

As of Amendment 9, the Follow-Up Period will consist of the Off-Tx Visit. No further visits will be conducted. The sponsor has decided to terminate survival follow-up for all subjects currently in survival follow-up.

Survival follow-up data will no longer be collected after the Off-Tx Visit and after 30 days from the last dose of study drugs.

The Follow-up Period consists of the Off-Tx Visit and the Follow-up Visits.

- The Off-Tx Visit will occur within 30 days after the last dose of study treatment. It applies to the Phase 1b subjects who discontinued study treatment early, before completing Cycle 1, and to the Phase 2 subjects who discontinued study treatment early, before completing 8 cycles. Following the completion of the Off-Tx Visit, subjects will transition to the Follow-up Period of the Extension Phase.
- In the Follow-up Period, subjects will be treated by the investigator according to the prevailing local standard of care. Subjects will be followed every 12 weeks (± 1 week) for survival, with tumor assessments performed as detailed in the Schedule of Procedures/Assessments, and subsequent anticancer treatments. Follow-up Visits continue as long as the study subject is alive unless the subject withdraws consent or until the sponsor terminates the study. The sponsor may decide to terminate survival follow-up anytime during the Extension Phase or when all subjects have discontinued study treatment.

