9.5.1.5.1 ADVERSE EVENTS AND EVENTS ASSOCIATED WITH SPECIAL SITUATIONS

An AE is any untoward medical occurrence in a patient or clinical investigation subject administered an investigational product. An AE does not necessarily have a causal relationship with the medicinal product. For this study, the investigational products are lenvatinib and pembrolizumab.

The criteria for identifying AEs in this study are:

- Any unfavorable and unintended sign (including an abnormal laboratory finding), symptom, or disease temporally associated with the use of an investigational product, whether or not considered related to the investigational product (Note: Every sign or symptom should not be listed as a separate AE if the applicable disease [diagnosis] is being reported as an AE.)
- Any new disease or exacerbation of an existing disease. However, worsening of the primary disease should be captured under efficacy assessments as disease progression rather than as an AE.
- Any deterioration in nonprotocol-required measurements of a laboratory value or other clinical test (eg, ECG or x-ray) that results in symptoms, a change in treatment, or discontinuation of study drug
- Recurrence of an intermittent medical condition (eg, headache) not present pretreatment (Baseline)
- An abnormal laboratory test result should be considered an AE if the identified laboratory abnormality leads to any type of intervention, withdrawal of study drug, or withholding of study drug, whether prescribed in the protocol or not.

All AEs observed during the study will be reported on the CRF. All AEs, regardless of relationship to study drug or procedure, should be collected beginning from the time the subject signs the study ICF and for 30 days after the last dose of study treatment. Subjects who fail screening primarily due to AE(s) must have the AE(s) leading to screen failure reported. SAEs will be collected for 90 days after the last dose or 30 days following the last dose if the subject initiates new anticancer therapy, whichever is earlier. An AE will not be reported on the Adverse Event CRF if other anticancer treatment is started. All SAEs will be reported on the Adverse Event CRF. All deaths will be collected for 30 days following the last dose of study treatment and reported on the Survival CRF.

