9.7.1.6.2 SECONDARY EFFICACY ANALYSES

The following secondary efficacy analyses will be performed on the data collected from the

Phase 2 portion of the study for each treatment cohort.

ORR: ORR and corresponding 95% CI based on exact binomial distribution will be estimated for each treatment cohort.

PFS: The distribution of PFS will be estimated using Kaplan–Meier methodology. Median time to PFS and 95% CI will be provided for each treatment cohort. Three-month, 6-month, 9-month, and 1-year PFS rate will be estimated using the Kaplan–Meier method and corresponding 95% CIs will be provided.

OS (overall survival): All events of death will be included, regardless of whether the event occurred while the subject was still taking study drug, or after the subject discontinued study drug. If a subject has no record of death, then the data will be censored at the date the subject was last known to be alive, or the data cutoff date, whichever is earlier. The distribution of OS will be estimated using Kaplan–Meier methodology. Median survival time and the corresponding 95% CI, survival rates at 12, 18, and 24 months, and corresponding 95% CIs will be estimated using Kaplan–Meier method for each treatment cohort.

DCR: Disease control rate and exact 95% CI will be estimated for each treatment cohort.

CBR: Clinical benefit rate and exact 95% CI will be estimated for each treatment cohort.

DOR: The distribution of the duration of response will be estimated using Kaplan–Meier Methodology. Median DOR and 95% CI will be provided for each treatment cohort.

Durable SD rate: DSDR and exact 95% CI will be estimated for each treatment cohort.

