- If a subject did not have a baseline tumor assessment (No. 1), the subject will be censored on the

date of first dose.

- If the subject died within 97 days (14 weeks -1 day) following first dose and did not receive a new anticancer treatment, it will be counted as PFS event at the date of death.
- If a subject had new anticancer treatment before PD or death (No. 4), the subject will be censored on the date of the last adequate tumor assessment prior to or on the date of new anticancer treatment.
- If a subject missed two or more tumor assessments before PD or death (No. 7), the subject will be censored on the date of the last adequate tumor assessment before PD or death. Note that if a subject is censored by both this criterion and the anticancer treatment criterion, the earliest censoring date will be used.
- Otherwise, if a subject had an event (No. 2, No. 5, or No. 6), the earliest event date will be used.

2. If a subject did not have PD or death, the censoring date will be the earliest censoring date if the subject met multiple censoring criteria (No. 1, No. 3, No. 4, No. 7).

The distribution of PFS and time curve will be estimated using Kaplan–Meier method. Median time to PFS and 95% CI will be provided for each cohort. Three-month, 6-month, 9-month, and 12-month PFS rate will be estimated using the Kaplan–Meier method and corresponding 95% CIs will be provided.

Overall Survival (OS): OS is measured from the start date of the treatment phase until date of death from any cause. All events of death will be included, regardless of whether the event occurred while the subject was still taking study drug, or after the subject discontinued study drug. If a subject has no record of death, then the data will be censored at the date the subject was last known to be alive, or the data cutoff date, whichever is earlier (see Table 6 for censoring rules). The distribution of OS and time curve will be estimated using Kaplan–Meier method. Median survival time and the corresponding 95% CI, survival rates at 12, 18, and 24 months, and corresponding 95% CIs will be estimated using Kaplan–Meier method for each treatment cohort.

Table 6 Censoring Rules for Overall Survival Endpoint

Situation	Event Date or Censoring	Outcome
Death during study	Date of death	Death
Death after data cut-off	Date of data cut-off	Censored
Subject still alive at data cut-off	Date of data cut-off	Censored

Situation	Event Date or Censoring	Outcome

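### OS is still planned at 12, 18 and 24 months from all deaths, but Amendment 09 ends death collection 30 days after last dose, so an OS cut after it could overstate late survival in late enrollees

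*Protocol*

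**What the plan says.** **Analysis.** Protocol 9.7.1.6.2 estimates OS by Kaplan-Meier for each cohort: "All events of death will be included, regardless of whether the event occurred while the subject was still taking study drug" or after it was stopped. The outputs are "Median survival time and the corresponding 95% CI, survival rates at 12, 18, and 24 months". SAP 5.4.3 repeats the all-deaths rule and the same three landmarks.

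**Collection.** Subjects were followed every 12 weeks for survival after stopping treatment. As of Amendment 09, protocol 9.1.3.2 states "The sponsor has decided to terminate survival follow-up for all subjects currently in survival follow-up" and "Survival follow-up data will no longer be collected after the Off-Tx Visit and after 30 days from the last dose of study drugs". Section 9.5.1.5.1 agrees: "All deaths will be collected for 30 days following the last dose of study treatment and reported on the Survival CRF". So does section 9.1: "After the end of the safety follow-up period, no data will be collected subsequently".

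**Censoring.** Protocol 9.7.1.1.2 and SAP 5.1.2 censor at the date last known alive. Protocol 9.7.1.6.2 and the running text of SAP 5.4.3 use the earlier of that date and the data cutoff. SAP Table 6 differs: its row "Subject still alive at data cut-off" censors at the cutoff date. Its lost-to-follow-up row uses the date last known alive. No row covers follow-up ended by the sponsor.

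**Timing.** SAP section 3 says the SAP rests on Amendment 08, so it predates the stop. Protocol 9.7 places all statistical analyses after study completion and database lock. Neither document says where the OS cutoff falls relative to Amendment 09.

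**The concern.** The OS estimand needs deaths that the current protocol no longer collects. A subject who stops treatment after Amendment 09 can contribute a death only within 30 days of the last dose and is censored after that. Confirmed progression is a protocol reason for stopping, so this censoring is linked to prognosis, whereas Kaplan-Meier assumes that censored subjects have the same future risk as those still observed. If risk rises after stopping, the curve is too high.

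Table 6 adds a second route. A subject whose follow-up was ended by the sponsor, and who has no recorded death, could be read as still alive at the cutoff and credited with event-free time that nobody observed.

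At stake are the later OS landmarks. In a single-arm study these would be read against outside data.

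**Working it through.** The plan gives no OS event count, power or expected rate, so there is no figure to reproduce. The check has two parts: who is exposed, and how large the effect could be.

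**1. Who is exposed.** Amendment 09 acts prospectively. A subject already in survival follow-up keeps every death and contact recorded before it and is censored near Amendment 09, not at treatment stop. For anyone first dosed more than *t* months before Amendment 09, status at *t* months was determined under the old 12-weekly follow-up, so the landmark at *t* is unaffected. What remains is later enrollees, later landmarks, and subjects stopping around or after the amendment.

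**2. Model (assumptions, not from the documents).** Time to treatment stop T is exponential with median 7 months, and survival after stopping is exponential with median 9 months. Time F from first dose to Amendment 09 is uniform over a stated range, and the data cut is 18 months after Amendment 09. Censoring as written: at F if T + 30 days < F; otherwise at the earlier of T + 30 days and F + 18 months.

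True OS has a closed form. With a = ln 2/7 = 0.0990 and b = ln 2/9 = 0.0770 per month,

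S(t) = (b·e^(−at) − a·e^(−bt)) / (b − a).

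At 12 months this is (0.0770 × 0.3047 − 0.0990 × 0.3968) / (−0.0220) = 71.9%. At 18 and 24 months it is 53.6% and 38.4%.

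**3. Results at 12/18/24 months, Amendment 09 as written** (simulated Kaplan-Meier, with noise of about 0.1 point)

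| Follow-up before Amendment 09 | Estimated OS, % | Minus true, points |
|---|---|---|
| 6-18 months | 74.1/64.1/61.4 | about +2/+10/+23 |
| 12-24 months | 71.8/55.3/46.2 | about 0/+2/+8 |
| 16-40 months | 71.8/53.7/39.2 | about 0/0/+1 |
| 24-48 months | same as true | none |

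**4. Limiting case.** Suppose every subject were censored 30 days after stopping, as if Amendment 09 had applied from first enrolment. With w = 30 days = 0.986 month and k = (e^((a−b)w) − 1)/(a − b) = 0.996, the death rate among those still observed settles at b·ak/(1 + ak) = 0.0770 × 0.0987/1.0987 = 0.00692 per month. Then S(t) ≈ exp(−0.00692 (t − w/2)), or 92.3/88.6/85.0%. This is an upper bound for this censoring, not an estimate for this trial.

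**5. Milder hazards.** The model in step 2 has no deaths on treatment, so its contrast is sharp. A second set assumes a median of 8 months on treatment and a death hazard of 0.02 per month while on it:

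- Off-treatment hazard 0.04: +0.6/+2.9/+6.8 points with 6-18 months of prior follow-up, and 0/+0.4/+2.3 with 12-24.
- Off-treatment hazard 0.08: +1.5/+6.5/+13.2 with 6-18 months.
- Either hazard with 16-40 months: at most +0.5 at 24 months.
- Equal hazards on and off treatment: within 0.1 point in every case.

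**6. Table 6.** Treat subjects whose deaths were not collected as alive to the cutoff, with 12-24 months of prior follow-up. The overstatement becomes about 0/+4/+15 points under step 2. Under step 5 with hazard 0.04 it is 0/+2.6/+9.9 (72.0/61.5/57.3 against 72.0/58.9/47.4). It persists with equal hazards: 78.7/71.3/68.3 against 78.7/69.7/61.8, or 0/+1.6/+6.5. This part therefore does not depend on risk rising after treatment stops.

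**7. Cutting at Amendment 09.** With hazard 0.04 and 12-24 months of prior follow-up, a cut at the amendment gives 72.0/58.9/47.6% against 72.0/58.9/47.4% with full follow-up, so the bias is gone. A landmark beyond the longest follow-up, such as 24 months when follow-up is 6-18 months, cannot then be estimated.

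**The case against.** The strongest reply is that no OS cut after Amendment 09 is planned. Protocol 9.1 sets each Phase 2 cohort's cutoff when evaluable subjects have completed 8 cycles or stopped early. Section 9.3.3 lets the sponsor halt survival follow-up after the primary study analysis. The revision history's rationale for ending tumor assessments refers to a completed primary endpoint analysis, and section 9.5.1.3 already speaks of a cutoff for the final efficacy analysis. These passages point to an earlier cut, but none fixes the cutoff for OS, and protocol 9.7 does not exclude a later one. Also, 8 cycles is 24 weeks, so a cut at that point could not supply 12- to 24-month OS for the last subjects enrolled.

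A reader might infer that any cut after Amendment 09 is biased, with OS near 85% at 24 months when the truth is 38%. The documents do not support that. It requires censoring everyone 30 days after stopping, whereas follow-up ended only prospectively. Amendments 07 and 08 are dated 19 April 2019 and 24 August 2020, 16.2 months apart, and Amendment 09 is later still, so many subjects may be past the landmarks that matter.

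It is also fair to say that the SAP's silence reflects sequence, that its running text already has the right censoring rule, that OS is a secondary endpoint with no formal comparison, and that higher risk off treatment is not stated anywhere. These points limit the size of the problem. They do not remove the mismatch between the OS text and the collection rules, or between Table 6 and the SAP's own text.

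**Conclusion.** The inconsistency is real and sits in current text: OS counts all deaths, while collection stops 30 days after last dose. Whether it biases a reported result depends on where OS is cut, which the documents leave open. If the cut falls at or before the follow-up stop, this source of bias is absent. If it falls later, the overstatement runs from none (24 months or more of prior follow-up) to about +23 points at 24 months (6-18 months of prior follow-up) under the 7- and 9-month medians, and is smaller under milder hazards. Table 6, applied to subjects no longer followed, makes it larger.

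The actual size cannot be computed, because the date of Amendment 09 and the enrolment dates are not in the text available. The late RCC enrollees are probably the most exposed. The sponsor's decision to end follow-up is not in question; the point is that the analysis text should match it. The correction should be made, since it costs little.

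**What to change.** - In protocol 9.7.1.6.2 and SAP 5.4.3, set the OS data cutoff for each cohort at or before the Amendment 09 follow-up stop, and state that OS will not be updated with data collected afterwards. If OS is already frozen at an earlier cutoff, giving that date is enough.
- Amend SAP Table 6 so that a subject without a recorded death is censored at the earlier of the date last known alive and the data cutoff, as the SAP text already says.
- Add a Table 6 row for follow-up ended by the sponsor under the same rule, and report by cohort how many subjects are censored for that reason.

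The cost is a sentence in each document and a table edit. The downside is that there is no later OS update, and a landmark beyond the follow-up available at the cutoff would be reported as not estimable.

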9.2 Discussion of Study Design

The study design follows well-established designs for Phase 1b/2 oncology studies, including ongoing studies featuring co-administration of oncology drugs with different mechanisms of action and PD-1 inhibitors. The design allows for rapid identification of tumors types which will respond to the combination of a TKI with a PD-1 inhibitor. The tumor types to be studied in this study (NSCLC, renal cell carcinoma, EC, UC, HNSCC, or melanoma) have shown response to lenvatinib and/or a PD-1 inhibitor in other studies where the drug products were individually administered.

9.3 Selection of Study Population

Subjects who do not meet all of the inclusion criteria or who meet any of the exclusion criteria will not be eligible to receive study drug. The subjects from Phase 1b and Phase 2 will be enrolled at up to 25 sites from the US and the EU.

Phase 1b - Depending on the number of dose levels explored, Phase 1b will enroll between 10 and 30 evaluable subjects with selected solid tumors.

Phase 2 may enroll approximately 20 subjects in each cohort. The EC and the RCC cohorts may be further expanded to approximately 120 and 145 evaluable subjects, respectively.

9.3.1 Inclusion Criteria

Subjects must meet all of the following criteria to be included in this study:

1. Phase 1b: Histologically and/or cytologically confirmed metastatic selected solid tumor types that have progressed after treatment with approved therapies or for which there are no standard effective therapies available. If nivolumab or pembrolizumab is an approved therapy for the subject's tumor type, but the subject has not been treated with it, the Investigator may enroll the subject in this study.

Phase 2: Histologically and/or cytologically confirmed metastatic selected solid tumor types with 0-2 prior lines of systemic therapy. If previously treated, subject has progressed after previous treatment.

As of Amendment 03, for the NSCLC and melanoma cohorts, subjects must have progressed on or after prior treatment with one anti-PD-1, anti-PD-L1, or anti-PD-L2 agent.

As of Amendment 05, for the RCC cohort, subjects are either treatment naïve or must have progressed on treatment with an anti-PD-1/PD-L1 mAb administered either as monotherapy, or in combination with other checkpoint inhibitors or other therapies.

As of Amendment 06, for the RCC cohort, all subjects must have progressed on treatment with an anti-PD-1/PD-L1 mAb administered either as monotherapy, or in combination with other checkpoint inhibitors or other therapies, and as of Amendment 07, the regimen with an anti-PD-1/PD-L1 mAb must be the most recent therapy. PD-1 treatment progression is defined by meeting all of the following criteria:

- a. Has received at least 2 doses of an approved anti-PD-1/PD-L1 mAb
- b. Has demonstrated disease progression after PD-1/PD-L1 as defined by RECIST v1.1. The initial evidence of PD is to be confirmed by a second assessment no less than 4 weeks from the date of the first documented PD
- c. Progressive disease has been documented within 12 weeks from last dose of anti-PD-1/PD-L1 mAb (refractory disease) or ≥ 12 weeks from last dose of anti-PD-1/PD-L1 mAb (late relapses)

Selected tumor types of both phases: NSCLC, predominantly clear cell renal cell carcinoma, EC, UC, squamous cell carcinoma of the head and neck, or melanoma (excluding uveal melanoma).

2. Life expectancy of 12 weeks or more
3. Phase 2: Measurable disease meeting the following criteria:
 - a. At least 1 lesion of ≥ 10 mm in the longest diameter (LDi) for a non-lymph node or ≥ 15 mm in the short-axis diameter for a lymph node that is serially measurable according to irRECIST using computerized tomography/magnetic resonance imaging (CT/MRI).
 - b. Lesions that have had external beam radiotherapy or loco-regional therapies such as radiofrequency) ablation must show subsequent evidence of substantial size increase to be deemed a target lesion.

4. Subjects must have an Eastern Cooperative Oncology Group (ECOG) Performance Status (PS) of 0 to 1.
5. Adequately controlled blood pressure (BP) with or without antihypertensive medications, defined as BP $\leq 150/90$ mmHg at screening and no change in antihypertensive medications within 1 week prior to the C(C) 1 D1.
6. Adequate renal function defined as creatinine $\leq 1.5 \times$ (upper limits of normal (ULN) or calculated creatinine clearance ≥ 40 mL/min per the Cockcroft and Gault formula with creatinine levels $> 1.5 \times$ ULN.
7. Adequate bone marrow function:
 - Absolute neutrophil count (ANC) $\geq 1500/\text{mm}^3$ ($\geq 1.5 \times 10^3/\mu\text{L}$)
 - Platelets $\geq 100,000/\text{mm}^3$ ($\geq 100 \times 10^9/\text{L}$)
 - Hemoglobin ≥ 9.0 g/dL
8. Adequate blood coagulation function as evidenced by an International Normalized Ratio (INR) ≤ 1.5 .
9. Adequate liver function as evidenced by bilirubin ≤ 1.5 times the ULN and alkaline phosphatase (ALP), alanine aminotransferase (ALT), and aspartate aminotransferase (AST) $\leq 3 \times$ ULN (in the case of liver metastases $\leq 5 \times$ ULN). In case ALP is $> 3 \times$ ULN (in the absence of liver metastases) or $> 5 \times$ ULN (in the presence of liver metastases) AND the subject also is known to have bone metastases, the liver specific ALP isoenzyme must be separated from the total and used to assess the liver function instead of the total ALP.
10. Males or females age ≥ 18 years at the time of informed consent.
11. Subjects with known brain metastases will be eligible if they have completed the primary brain therapy (such as whole brain radiotherapy, stereotactic radiosurgery or complete surgical resection) and if they have remained clinically stable, asymptomatic and off of steroids for at least 28 days before starting study treatment.
12. All females must have a negative serum or urine pregnancy test (minimum sensitivity 25 IU/L or equivalent units of beta-human chorionic gonadotropin [β -hCG]) at the Screening Visit and the Baseline Visit. A pregnancy test needs to be performed within 72 hours of the first dose of study drug. Females of childbearing potential* must agree to use a highly effective method of contraception for the entire study period and for 120 days after study discontinuation, ie:
 - total abstinence (if it is their preferred and usual lifestyle)
 - an intrauterine device (IUD) or hormone-releasing system (IUS)

- a contraceptive implant
- an oral contraceptive** (with additional barrier method)

OR

- have a vasectomized partner with confirmed azoospermia.

For sites outside of the EU, it is permissible that if a highly effective method of contraception is not appropriate or acceptable to the subject, then the subject must agree to use a medically acceptable method of contraception, ie, double barrier methods of contraception such as condom plus diaphragm or cervical/vault cap with spermicide.

NOTES:

*All females will be considered to be of childbearing potential unless they are postmenopausal (amenorrheic for at least 12 consecutive months, in the appropriate age group, and without other known or suspected cause) or have been sterilized surgically (ie, bilateral tubal ligation, total hysterectomy, or bilateral oophorectomy, all with surgery at least 1 month before dosing).

**Must be on a stable dose of the same oral hormonal contraceptive product for at least 4 weeks before dosing with study drug and for the duration of the study.

13. Male subjects who are partners of women of childbearing potential must use a condom + spermicide and their female partners if of childbearing potential must use a highly effective method of contraception (see methods described in [Inclusion Criterion #12](#)) beginning at least 1 menstrual cycle prior to starting study drug(s), throughout the entire study period, and for 120 days after the last dose of study drug, unless the male subjects are totally sexually abstinent or have undergone a successful vasectomy with confirmed azoospermia or unless the female partners have been sterilized surgically or are otherwise proven sterile.
14. Voluntary agreement to provide written informed consent and the willingness and ability to comply with all aspects of the protocol.
15. Archival tumor tissue or a newly obtained biopsy must be available prior to the first dose of study drug for biomarker analysis. In the case archival tissue cannot be provided, patients with inaccessible tumors for biopsy specimens can be enrolled without a biopsy upon consultation and agreement by the sponsor.
Note: In case of submitting unstained cut slides, freshly cut slides should be submitted to the testing laboratory within 14 days from when the slides are cut. See [Section 9.5.1.4.2](#) in the protocol for an explanation.

